## 2.2 Primary Objective and Endpoints

Primary Objective	Endpoints	Time Frame
To determine the composite response rate (achieving one or more of the endpoints) of apalutamide plus cetrelimab.	

PSA50 (decline from baseline in serum PSA of <math>\geq 50\%</math>, confirmed by repeat measurement <math>\geq 4</math> weeks later)* AND/OR

Objective response by RECIST 1.1 criteria**

	From initiation of study treatment until discontinuation of treatment (maximum of 2 years).

\* to be considered evaluable for PSA50 response, patients must have baseline PSA level  $> 2$  ng/mL

\*\* to be considered evaluable for objective response, patients must have measurable soft tissue disease by RECIST 1.1 criteria on baseline scan assessment

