## 2.3 Secondary Objectives and Endpoints

Secondary Objective	Endpoints	Time Frame
1. To determine safety of the combination of apalutamide and cetrorelimab	
 
Proportion of participants with treatment-related AEs, as graded by National Cancer Institute Common Terminology Criteria for Adverse Events (NCI CTCAE version 5.0)
 
	From initiation of study treatment until treatment discontinuation.
2. To determine the median radiographic progression-free survival by PCWG3 criteria	
 
Median progression free survival by PCWG3 criteria.
 
	From initiation of study treatment until radiographic progression by PCWG3 criteria or death, whichever occurs first.
3. To determine the PSA50 and PSA90 response proportion.	
 
<math>\geq 50\%</math> and <math>\geq 90\%</math> decline from baseline in PSA, respectively, confirmed by repeat measurement <math>\geq 4</math> weeks after first time point*
 
	From initiation of study treatment until maximal decline in serum PSA during study treatment.
4. To determine the median PSA progression-free survival.	
 
Median PSA progression-free survival by PCWG3 criteria.
 
	From initiation of study treatment until PSA progression by PCWG3 criteria or death, whichever occurs first.
5. To determine the median overall survival.	
 
Median overall survival from date of start of protocol treatment until death from any cause.
 
	From initiation of study treatment until death from any cause. (3 years)
6. To determine the objective response rate by RECIST 1.1 criteria	
 
Objective response rate by RECIST 1.1 criteria.
 
Median duration of response
 
	From initiation of study treatment until maximal percent decline from baseline in SLD of target lesions.

\* To be considered evaluable for this endpoint, patients must have baseline PSA level  $> 2$  ng/mL.

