#### 6.3.3 End-of-Treatment Study Procedures

- Clinical Assessments
  - Physical examination (including weight), may be done via a telemedicine visit
  - Vital Signs (BP and heart rate)
  - AE assessment
  - Performance status
- Laboratory Assessments
  - Hematology labs - CBC with differential and platelet count

- Blood chemistry assessment, including: ALP, ALT/AST, total bilirubin, calcium, BUN, creatinine, potassium, sodium, chloride, bicarbonate
- Thyroid function tests - including thyroid-stimulating hormone (TSH), reflex free T4, reflex total/free T3
- Serum PSA
- Whole blood peripheral immune markers
- Isolation of peripheral blood mononuclear cells (PBMC)
- Circulating tumor cells
- Circulating tumor DNA
- Tissue Collection/Biopsy (optional)
  - Tumor Tissue Collection: A CT-guided core biopsy is optional at End of Treatment. The same lesion that was biopsied during Screening should be biopsied whenever feasible.

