### **6.4 Correlative Studies**

#### **6.4.1 Metastatic Tumor Biopsy**

Metastatic tumor biopsies are only required if the patient has no previous metastatic biopsy (within 90 days of C1D1 without intervening systemic therapy).

Metastatic tumor biopsy at Screening is optional.

Assays to be performed include RNA-seq, targeted genomic sequencing, histological assessment, and tumor content permitting, additional IHC and/or DNA-seq.

Metastatic tumor biopsy is optional at PD.

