### 8.3.4 Exploratory/Correlative Analysis/Assessments

Exploratory Objective 1 Analysis: To explore the association between baseline metastatic tumor characteristics including t-SCNC, AR, RB1 loss, and immune response transcriptional signatures with clinical outcomes

Exploratory Objective 2 Analysis: To evaluate objective response rate and median progression-free survival by irRECIST criteria

Exploratory Objective 3 Analysis: To evaluate the association between immune related AEs (irAEs) and clinical efficacy outcomes

Exploratory Objective 4 Analysis: To evaluate the association between baseline and change from baseline in circulating T cell and myeloid cell subsets with clinical outcomes

Exploratory Objective 5 Analysis: To explore the mechanism of skin rash in patients receiving combination of apalutamide plus cetrelimab

Exploratory Objective 6 Analysis: To explore the association between genomic and epigenomic features of circulating tumor DNA with clinical outcomes

Exploratory Objective 7 Analysis: To explore the association between circulating tumor cell (CTC) characteristics including heterogeneity, overall CTC count, and expression of markers of interest (AR, CD56, cytokeratin) with clinical outcomes

Quantification of circulating T cell subsets will be performed using mass cytometry analysis of whole blood. The percent change from baseline in the circulating T cell subsets will be reported using descriptive statistics (e.g. median, range, standard deviation). In an exploratory fashion, the study cohort will be dichotomized by those with percent change from baseline above and below median and efficacy outcomes will be compared between dichotomized subgroups using log-rank test for time-to-event endpoints (e.g. PFS, duration of response) and Fisher's exact test for categorical variables (e.g. composite response rate, objective response rate, PSA50 response rate).

Baseline metastatic tumor biopsies will be evaluated for following biomarkers of interest:

- Genomic alterations by targeted next-generation sequencing including presence of *RB1* loss
- Transcriptional profiling and application of previously validated signatures and specific genes implicated with immune response, t-SCNC, *RB1* loss, and AR activity
- Histologic assessment for t-SCNC morphology
- When feasible, immunohistochemical analysis to identify PD-L1 expression level and tumor infiltrating lymphocytes

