As of Protocol Amendment 1.8 dated 07-24-2023, the italicized analyses below will no longer be performed. Epic Sciences is no longer involved in sample analysis and will return UCSF samples back to UCSF.

*Circulating tumor cells be analyzed using the Epic Sciences' platform for the following biomarkers of interest:*

- *Heterogeneity score*
- *NEPC probability using previously published prediction tool (Beltran et al. CCR 2015)*
- *Enumeration*
- *Expression of AR, CD56, cytokeratin, and RB1 using IF assays*

Circulating tumor DNA will be analyzed by the [name] laboratory at UCSF for the following biomarkers of interest:

- Genomic alterations by targeted next-generation sequencing including presence of *RB1* loss
- Inference of gene expression of target genes of interest, including AR, EZH1, ASCL1, using 5-hydroxymethyl cytosine (5-hmC) sequencing of ctDNA

The association between the above tissue-based biomarkers (baseline and change from baseline) with clinical efficacy endpoints including PFS, ORR, PSA50, and overall survival will be analyzed using log-rank test for time-to-event endpoints (e.g. PFS, duration of response) and Fisher's exact test for categorical variables (e.g. composite response rate, objective response rate, PSA50 response rate).

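### Tissue change from baseline is to be tested against PFS and response, but the second biopsy comes only at end of treatment or progression, after those outcomes are settled

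*Combined protocol and SAP*

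**What the plan says.** Section 8.3.4 closes its biomarker plan by committing to analyse "The association between the above tissue-based biomarkers (baseline and change from baseline) with clinical efficacy endpoints including PFS, ORR, PSA50, and overall survival". The method follows in the same sentence: these associations "will be analyzed using log-rank test for time-to-event endpoints (e.g. PFS, duration of response) and Fisher's exact test for categorical variables", with composite response among the categorical examples. No landmark, time-dependent covariate or descriptive-only handling is given for change values.

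Earlier in 8.3.4 the tissue assays are introduced with "Baseline metastatic tumor biopsies will be evaluated for following biomarkers of interest". Exploratory Objective 1 (2.4, repeated in 8.3.4) is likewise confined to baseline tumour characteristics.

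On collection, the study calendar (6.1) marks tumour tissue at Screening and End of Treatment only. Section 6.3.3 says "A CT-guided core biopsy is optional at End of Treatment", and 6.4.1 says "Metastatic tumor biopsy is optional at PD". For most patients the first sample is also elective: "Metastatic tumor biopsy at Screening is optional" (6.4.1), with a biopsy required only where no suitable earlier one exists and a lesion is safely accessible.

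**The concern.** A log-rank comparison from first dose assumes that group membership is known at first dose, or at least before follow-up for the endpoint begins. Here the group would be assigned by a sample taken when follow-up for PFS and response has already ended. Patients who stay on therapy longer have the second biopsy later, so any marker that drifts with time on treatment will separate long from short PFS even if it has no bearing on progression.

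The comparison would also rest on few, selected patients, since both biopsies are largely optional and those who die or deteriorate may have no second sample. At stake is how a correlative result from a 24-patient trial is read. A tissue-change finding reported with a PFS p-value could be carried into later work as a prognostic or predictive marker when the design cannot show that.

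**Working it through.** The plan gives no figure for this analysis, so the check is mainly one of timing, followed by an illustration.

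**1. When is a tissue change value available, and when do the endpoints close?**

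- *Tissue change:* needs the End of Treatment or PD biopsy (6.1, 6.3.3, 6.4.1). No on-treatment tumour biopsy is scheduled before that.
- *Composite response (2.2):* assessed "From initiation of study treatment until discontinuation of treatment (maximum of 2 years"). It closes when treatment stops, which is when the second biopsy falls due.
- *Radiographic PFS (2.3):* runs "From initiation of study treatment until radiographic progression by PCWG3 criteria or death, whichever occurs first".
- *PFS censoring (8.3.3, under Secondary Objective 4):* patients who stop for reasons such as an AE or withdrawal are censored at last treatment, so their PFS time has also ended by the biopsy.
- *Overall survival (2.3):* continues after the biopsy, so the outcome is still open, but the clock started at first dose.

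**2. The gap in days, for a patient who progresses at the first scan.** Cycles are 28 days, so C4D1 is day 3 × 28 + 1 = 85. With the −14 day window the scan falls on days 71–85. Progression is dated to that scan (7.1.4), and treatment may continue until a confirmatory scan at least 4 weeks later (3.5), that is day 99 or later. The PFS event can therefore precede an End of Treatment biopsy by four weeks or more.

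**3. Contrast with ctDNA.** Plasma is drawn at C1D1, C2D1, C3D1 and End of Treatment (6.4.4). C2D1 is day 29 and C3D1 is day 2 × 28 + 1 = 57, both before day 71. A ctDNA change can be known before the first scheduled scan; a tumour-tissue change cannot.

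**4. Overall survival.** Only patients alive at the second biopsy have a change value, so none of them can have died between first dose and that biopsy. The length of this guaranteed-survival interval is roughly time on treatment, and it will differ between groups if the marker drifts with time.

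**5. Illustration of size.** Assumptions, none of them stated in the plan for tissue: 8–16 paired biopsies; every patient has a PFS event; exponential PFS (median 5 months, which does not affect the result); groups split at the median change; two-sided 0.05. Generate

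change = ρ × standardised log(PFS time) + √(1 − ρ²) × noise,

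so the marker does not influence PFS but its change drifts with time on therapy.

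| Correlation ρ | Log-rank rejection rate, 8–16 pairs |
|---|---|
| 0 | about 6–7% |
| 0.3 | about 9–15% |
| 0.5 | about 17–32% |
| 0.7 | about 33–61% |

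The table standardises log time within each data set. Standardising to the population gives somewhat lower upper rows (16–29% at 0.5, 28–55% at 0.7). A separate version with correlation on the untransformed time scale shows the same pattern: at ρ = 0, 0.2, 0.4 and 0.6, about 7%, 10%, 18% and 34% with 12 pairs; with all 24 patients paired, 6%, 13%, 31% and 60%.

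Very small numbers remove the issue along with the analysis. With 4 pairs split two and two, the most extreme ordering gives observed 2, expected 2/4 + 2/3 + 1 + 1 = 3.167 and variance 0.25 + 0.222 = 0.472, so χ² = (2 − 3.167)² / 0.472 ≈ 2.88. That is below 3.84, and the test cannot reject.

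**The case against.** The strongest reply is that the plan speaks of association, not prediction. Log-rank and Fisher tests claim no direction, and asking whether tumours of long and short responders evolve differently is a fair exploratory question. This stands. A reader might infer that the plan reverses cause and effect, but 8.3.4 makes no causal or predictive statement. The fault is in what the result could be taken to mean.

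A reader might also call the simulated figures an inflated false-positive rate. They are not: drift builds in a real, non-causal association, and at zero correlation the test stays near its nominal size. They are rejection rates under an assumed drift. The number of pairs, complete PFS events and median cut are assumptions too. Section 8.3.4 specifies the median split for circulating T-cell subsets, and several tissue markers, such as RB1 loss and morphology, are categorical.

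The sentence may be drafting residue, or broader than tumour tissue, since it follows directly after the ctDNA list. If ctDNA is meant, it would be wrong to say that every change value arrives only at the end of treatment. The ambiguity is itself a reason to clarify the text.

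Finally, 8.3.1 already restricts correlative analyses to patients with evaluable samples, so missing pairs are not an unaddressed gap, though selection remains a limitation. The analysis carries no alpha and no decision rule.

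**Conclusion.** The timing point holds for tumour tissue against PFS, ORR, PSA50 and composite response. As scheduled, tissue change is known only when those outcomes are determined or censored, so the planned tests cannot support a prognostic or predictive reading. It does not extend in that form to overall survival, where grouping precedes death and the problem is immortal time. Nor does it extend to ctDNA, which has early on-treatment samples but would still need a landmark. The change wording also exceeds Exploratory Objective 1 and the assay list, and needs reconciling with them in any case.

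The possible size runs from negligible to a majority of data sets rejecting, depending on a drift correlation and a pair count that the documents do not give; the timing argument does not depend on either. The Simon design, the primary analysis and the safety rule are untouched. Severity is minor.

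**What to change.** In 8.3.4:

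- Limit the tests against PFS, ORR, PSA50, composite response and duration of response to baseline tissue biomarkers, in line with Exploratory Objective 1.
- Report paired End of Treatment/PD tissue change descriptively, with the number of pairs and the timing of the second biopsy. If an association with survival is wanted, count survival from the date of that biopsy.
- State whether tissue-based biomarkers is meant to include ctDNA. If so, analyse its change at C2D1 or C3D1 with a landmark at the sampling date, among patients still at risk for the endpoint then. PSA is measured at the same visits, so say how a PSA decline already reached by the landmark is handled.

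The cost is wording only, with no new samples or visits. One exploratory tissue-change test is dropped or re-anchored. The ctDNA analysis is a partial substitute, since plasma cannot replace tissue histology, PD-L1 staining or tumour-infiltrating lymphocyte measures.

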## The Lymphocyte Proliferation Assay to study mechanism of apalutamide induced rash

The lymphocyte proliferation assay (LPA) allows an assessment of the role of immunological reactions in drug-induced adverse reactions. The assay allows a measurement of the ability of lymphocytes placed in short-term tissue culture to undergo a clonal proliferation when stimulated in vitro by a foreign molecule, antigen or mitogen. Several studies have shown that CD4+lymphocytes proliferate in response to antigenic peptides in association with Class II MHC molecules on antigen-presenting cells. This proliferative response of lymphocytes to antigen in vitro occurs only if the patient has been immunized to that antigen, either by having recovered from an infection with the microorganism containing that antigen, or by having been vaccinated.

Therefore, some normal individuals may not respond to a given antigen, but most people will respond to at least one of several common microbial antigens.

This study will determine whether subjects who have experienced skin rash while on apalutamide have an apalutamide (metabolite) specific LPA response. Besides lymphocyte proliferation various other endpoints will be assessed on PBMCs like Elispot. If lymphocyte proliferation is observed, additional studies will be conducted to isolate the individual T-cell clones.

## 9 Study Management

### 9.1 Pre-study Documentation

This study will be conducted in accordance with the ethical principles that have their origin in the Declaration of Helsinki as stated in 21 CFR §312.120(c)(4); consistent with GCP and all applicable regulatory requirements.

Before initiating this trial, the PI will have written and dated approval from the Institutional Review Board for the protocol, written informed consent form, subject recruitment materials, and any other written information to be provided to participants before any protocol related procedures are performed on any participants.

The clinical investigation will not begin until either FDA has determined that the study under the Investigational Drug Application (IND) is allowed to proceed or the FDA has determined that the study is exempt from IND requirements.

The PI must comply with the applicable regulations in Title 21 of the Code of Federal Regulations (21 CFR §50, §54, and §312), GCP/ICH guidelines, and all applicable regulatory requirements. The IRB must comply with the regulations in 21 CFR §56 and applicable regulatory requirements.

### 9.2 Institutional Review Board Approval

The protocol, the proposed informed consent form, and all forms of participant-facing materials related to the study (e.g. advertisements used to recruit participants) will be reviewed and approved by the UCSF IRB. Prior to obtaining IRB approval, the protocol must be approved by the Helen Diller Family Comprehensive Cancer Center Site Committee and by the Protocol Review Committee (PRC). The initial protocol and all protocol amendments must be approved by the IRB prior to implementation.

### **9.3 Informed Consent**

All participants must be provided a consent form describing the study with sufficient information for each participant to make an informed decision regarding their participation. Participants must sign the IRB -approved informed consent form prior to participation in any study specific procedure. The participant must receive a copy of the signed and dated consent document. The original signed copy of the consent document must be retained in the medical record or research file.

### **9.4 Changes in the Protocol**

Once the protocol has been approved by the UCSF IRB, any changes to the protocol must be documented in the form of an amendment. The amendment must be signed by the PI and approved by PRC and the IRB prior to implementation.

If it becomes necessary to alter the protocol to eliminate an immediate hazard to participants, an amendment may be implemented prior to IRB approval. In this circumstance, however, the PI must then notify the IRB according to institutional requirements.

### **9.5 Handling and Documentation of Clinical Supplies**

The Principal Investigator will maintain complete records showing the receipt, dispensation, return, or other disposition of all investigational drugs at the site. The date, quantity and batch or code number of the drug, and the identification of participants to whom the investigational product has been dispensed by participant number and initials will be included.

The PI at each study site shall not make the investigational drug available to any individuals other than to qualified study participants. Furthermore, the PI at each study site will not allow the investigational product to be used in any manner other than that specified in this protocol.

### **9.6 Case Report Forms (CRFs)**

The PI and/or designee at each study site will prepare and maintain adequate and accurate participant case histories with observations and data pertinent to the study. Study specific Case Report Forms (CRFs) will document safety and treatment outcomes for safety monitoring and data analysis. All study data will be entered into OnCore® via standardized CRFs in accordance with the CTMS study calendar, using single data entry with a secure access account. Study personnel for each study site will complete the CRFs; the PI for the study site will review and approve the completed CRFs.

The information collected on CRFs shall be identical to that appearing in original source documents. Source documents will be found in the participant's medical records maintained by study personnel at each study site. All source documentation should be kept in separate research files for each participant.

In accordance with federal regulations, the PI at each study site is responsible for the accuracy and authenticity of all clinical and laboratory data entered onto CRFs. The PI will approve all completed CRFs to attest that the information contained on the CRFs is true and accurate.

The PI at each study site will be responsible for ensuring the accurate capture of study data. At study completion, when the CRFs have been declared to be complete and accurate, the database will be locked. Any changes to the data entered into the CRFs after that time can only be made by joint written agreement among the Study Chair and the trial statistician.

All source documentation and CTMS data will be available for review/monitoring by the UCSF DSMC and regulatory agencies.

## 9.7 Oversight and Monitoring Plan

The UCSF Helen Diller Family Comprehensive Cancer Center DSMC will be the monitoring entity for this study. The UCSF DSMC will monitor the study in accordance with the NCI-approved Data and Safety Monitoring Plan (DSMP). The DSMC will routinely review all AEs and suspected adverse reactions considered "serious". The DSMC will audit study-related activities to ensure that the study is conducted in accordance with the protocol, local standard operating procedures, FDA regulations, and Good Clinical Practice (GCP). Significant results of the DSMC audit will be communicated to the IRB and the appropriate regulatory authorities at the time of continuing review, or in an expedited fashion, as applicable. See Appendix 2 - Data and Safety Monitoring Plan.

